strength and type of Internet connections they have available to them. Using their personal computer, participants receive a link via email to a videoconference. The success of signing on and completing a short call via videoconference will serve several purposes. First, it will allow for the research team to determine how comfortable the participant and communication partner are with using a computer and email to start a video-chat. Secondly, the audio/video guality of the video-chat will be a good indicator of the participant and communication partner's strength and quality of Internet connection. During the session, participants and communication partners will also be asked to complete an Internet speed test (www.speedtest.net) to ensure their Internet bandwidth can support uninterrupted video-chat. Participants are required to have at least 1 Mbps upload and 4 Mbps download of available Internet bandwidth as recommended by the HIPAA compliant video-chat software program used in this study. A strong Internet connection is important to ensure uninterrupted Treatment Sessions with consistent audio and video feed. Insufficient Internet connection will be remedied prior to enrollment. A Technology Proficiency screening was implemented during our preliminary study and has been successful at identifying appropriate candidates for treatment over videoconference.

Cognitive Screening. A brief cognitive screening (about 30 minutes) will be administered to participants over videoconference. This assessment will serve to confirm mild impairment of PPA.

Depression Screening. Individuals will be given the 15-item Geriatric Depression Scale to screen for depression. Indications of depression are categorized into mild, moderate and severe as follows: 5-8 mild depression, 9-11 moderate depression, and 12-15 severe depression; Sheikh & Yesavage, 1986). If an individual scores a 9 or above and their depression is untreated, they will be ineligible for the study.

SLP Screening. The screening with the speech-language therapist will be the last screening activity. SLP's will confirm PPA subtype at this screening.

At any point during screening, a participant may be determined to be ineligible. They will be informed of the reason they are ineligible for the study. If a participant is eligible, they will be consented into the study and randomized to study group (experimental vs. control).

Inclusion/Exclusion Criteria:

- Must be English speakers

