Post-Intervention Evaluation 2: This evaluation will be identical to the **Post-Intervention Evaluation 1** in Block 1. This evaluation will take place approximately one week following the 5 weekly therapy sessions of Intervention Block 2. Identical to other evaluations, this will occur over two sessions lasting no more than 2 hours per session (4 hours in total).

12- month Evaluation: Approximately one year after the Baseline Evaluation, the participant will take part in a final evaluation. Post-treatment outcomes will be measured through standardized evaluation measures, communication participation measures, and language performance measures that have been given throughout the course of the study. Identical to other evaluations, this will occur over two sessions lasting no more than 2 hours per session (4 hours in total).

Scheduling Compliance:

Sessions: To successfully complete the trial, participants must complete 10 visits within 12 weeks for the first treatment block and 5 visits within 7 weeks for the second treatment block. Circumstances may arise that require the re-scheduling of visits. When this occurs, the following rules apply:

- No more than 2 visits may be scheduled within a 5-day window
- Sessions on consecutive days should be avoided

Visits that cannot be scheduled within these rules will be considered 'missed' visits. In the case of a missed visit, the visit will not be re-scheduled. Dosing effects resulting from missed visits will be accounted for in the statistical analyses. Participants with more than 2 missed visits will be asked if they would like to continue to receive the intervention as part of routine clinical care; however, the participant will be withdrawn from the study analysis.

6-Month and 12-Month Evaluations: These evaluations should be scheduled within a time window that includes the 2-weeks prior to or following the actual 6 or 12 month follow-up date.

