PROVISIONS TO MONITOR THE DATA TO ENSURE THE SAFETY OF PARTICIPANTS:

A data safety and monitoring board (DSMB) has been established for the proposed study. The members of this committee are not associated with the research project and work independently of the PI. They are all qualified to review the patient safety data generated by this study because of their unique expertise in the areas of statistics, speech-language therapy, primary progressive aphasia, dementia, treatment efficacy/outcomes and clinical trials. The committee will meet at least annually to review study data concerning recruitment, randomization, retention, compliance form completion, gender and minority inclusion, intervention effects and safety. The committee will be available at any time to advise on these issues.

At each meeting the committee will vote whether to continue the trial. Reasons for early termination of the study may include concerns about safety of the intervention or an early convincing beneficial effect of intervention. The committee may also recommend amendments to the study protocol if it appears that such are necessary for safety of scientific validity of the trial. Committee minutes will be part of annual Institutional Review Board review.

WITHDRAWAL OF PARTICIPANTS:

Participants can be withdrawn from the study for the following reasons: 1) Lost contact; 2) Missed visits due to: a) "no show" without rescheduling for two treatment sessions; or b) not adhering to scheduling compliance rules (see above); 3) Obtaining outside speech-language therapy during the study.

If individuals are withdrawn from the study, they will be sent a FedEx Airbill to send their laptop computer provided by the study back to Northwestern. They will be informed of the reasons why they were withdrawn. These reasons for possible withdrawal will be clearly stated in the consent form.

Data collected up until the point of lost contact with the participant will be used in analyses for the study.

RISKS TO PARTICIPANTS:

The risks for participation in the proposed research are minimal. Potential adverse events associated with this research include:

- 1. Loss of confidentiality
- 2. Fatigue and/or frustration in performing the online intervention
- 3. Depression and Anxiety: Caregivers of individuals with PPA and living with PPA can both be psychologically taxing experiences. It is not abnormal for individuals in these

Version Date: 04/16/2018

Page 12 of 18 HRP-593 / v011017

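### Randomised participants with more than two missed visits are removed from the analysis, so the primary 12-month comparison depends on attendance and is open to selection bias of unknown size and direction

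*Combined protocol and SAP*

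**What the plan says.** The rule is in Procedures Involved, Scheduling Compliance. The target is that "participants must complete 10 visits within 12 weeks for the first treatment block and 5 visits within 7 weeks for the second treatment block". A visit that cannot be placed within the rescheduling rules counts as missed and is not made up. Anyone who exceeds two such visits may choose to keep having sessions "as part of routine clinical care; however, the participant will be withdrawn from the study analysis". The same paragraph says: "Dosing effects resulting from missed visits will be accounted for in the statistical analyses". No method is named.

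Randomisation follows the last screening step (SLP Screening) and so precedes every treatment session. Specific Aim 2 Analysis makes baseline and 12 months the primary time points, and Power Calculation for Aim 2 describes a 12-month mean adjusted by analysis of covariance.

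Withdrawal of Participants lists reasons for which a person can be withdrawn. Under missed visits, item (a) is a no-show "without rescheduling for two treatment sessions", and item (b) is failure to follow the scheduling compliance rules, with a pointer back to them. The section closes: "Data collected up until the point of lost contact with the participant will be used in analyses for the study".

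**The concern.** Randomisation makes the arms comparable as assigned. Removing people for something they do after assignment can undo that, because those left in each arm may differ in prognosis. A 12-month difference could then partly reflect who was removed, in favour of either arm.

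The documents also leave open whether people removed from the analysis still have the 6- and 12-month evaluations. If those scores are never collected, the comparison of all randomised participants cannot be fully rebuilt later.

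**Working it through.** **1. The plan's own figure.** Inputs from Power Calculation for Aim 2 and Table 1: CCRSA SD 16, 51 and 34 per arm, two-sided alpha 0.017, 80% power. Detectable difference = 16 × √(1/51 + 1/34) × (2.387 + 0.842) = 16 × 0.2214 × 3.228 = 11.4, or 11.6 with the t distribution. The plan states 12, so the design figure reproduces. It assumes that those analysed are comparable as randomised.

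**2. Does other text restore the excluded participants?**
- The data-use sentence under Withdrawal of Participants speaks of lost contact. Someone who continues as routine care has not lost contact, so the sentence does not clearly cover them. If it is read to cover every withdrawal, it conflicts with Scheduling Compliance.
- The sentence on dosing effects names no analysis and cannot apply to people already removed.
- No section defines an all-randomised set or handles absent 12-month scores.

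**3. Illustrative bias.** Assumptions: no true effect; SD 16; baseline to 12-month correlation 0.50 (Power calculation for Aim 1); a normally distributed tendency to miss visits, the same in both arms, correlated r with a worse 12-month score and r0 with a worse baseline score; the share p with the highest tendency is excluded.

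Bias (experimental minus control) = (r − 0.5 × r0) × 16 × [λ(pE) − λ(pC)], where λ(p) = φ(z₁₋ₚ)/(1 − p).

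Low end: r = r0 = 0.3, multiplier 0.15. High end: r = 0.5, r0 = 0, multiplier 0.5. The residual SD is 16 × √(1 − 0.25) = 13.9. The starting arms are 54 and 36 (90 at 60:40, from Study Timelines and Study Design). SE = 13.9 × √(1/nE + 1/nC) with the numbers retained. Type I error is the two-sided rejection rate at critical value 2.387.

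| Excluded, experimental vs control | λ(pE) − λ(pC) | Bias, low to high end | SE | Type I error |
|---|---|---|---|---|
| 3 of 54 vs 2 of 36 (5.6% each) | 0 | 0 | 3.07 | 0.017 |
| 4 of 54 vs 1 of 36 | 0.1514 − 0.0656 = 0.0858 | +0.2 to +0.7 | 3.05 | 0.017 to 0.020 |
| 1 of 54 vs 4 of 36 | 0.0462 − 0.2131 = −0.1669 | −0.4 to −1.3 | 3.10 | 0.018 to 0.028 |
| 15% vs 5% | 0.2743 − 0.1086 = 0.1657 | +0.4 to +1.3 | 3.13 | 0.018 to 0.027 |
| 25% vs 5%, high end only | 0.4237 − 0.1086 = 0.3151 | +2.5 | 3.22 | 0.055 |

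The five exclusions come from the gap between 90 enrolled and 85 in the power calculation: 5/90 = 5.6%. Measured from the ceiling of 100, the gap is 15%. The documents do not call either a dropout allowance. A simulation at trial size (20,000 runs) gave slightly higher rejection rates: 0.022 for 4 vs 1 at the high end and 0.067 for 14 vs 2.

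Equal shares alone do not guarantee zero bias. Without covariate adjustment, 15% excluded in both arms with a 1 SD gap between retained and excluded people in one arm only gives 0.15 × 16 = 2.4 points, in either direction.

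**4. Counting basis.** The text does not say whether missed visits are counted per block or over all 15. Counted over 15, a person who attends 12 (80%) is removed. Counted per block, a person who misses 2 + 2 (11 of 15 attended) stays. If misses are independent at rates of 5.7%, 9.1% and 11.6% per visit, P(3 or more of 15) is 5.0%, 15.0% and 24.9%. Per block, 1 − P(≤2 of 10) × P(≤2 of 5) is 1.8%, 6.2% and 11.2%. The ratios are 2.8, 2.4 and 2.2. If misses cluster within persons (beta-binomial, intraclass correlation 0.1 to 0.3 assumed, matched to 5%, 15% and 25% over 15 visits), the ratios fall to between 1.8 and 1.3.

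**The case against.** The best defence is that the effect may be small. No missed-visit rate or arm difference is given. The rescheduling windows and the availability check at enrolment should keep missed visits few. Near the loss that the enrolment figures suggest, the illustrated bias is 0.2 to 1.3 points against a design difference of 12. The Background also calls this a pilot trial. All of this stands as a limit on the likely size. It does not change what happens to people who exceed the limit, and an allowance for loss would protect power, not comparability.

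Four stronger readings are tempting, but the documents do not support them:
- **The two sections set contradictory thresholds.** Item (b) under Withdrawal of Participants brings in the scheduling rules. Item (a) adds a separate, overlapping trigger, and the section says only that people can be withdrawn. How the triggers fit together is unclear, which is less than a contradiction.
- **Exclusion will differ by arm because partners must attend every session in one arm only.** No text makes a session missed when the partner is absent. Unequal exclusion is possible but not shown.
- **The counting basis changes the excluded share by 2.2 to 2.8 times.** That holds only if misses are independent, which sits badly with a bias model built on a personal tendency to miss visits.
- **Withdrawn people can simply be evaluated on their own equipment.** The text "Using their personal computer, participants receive a link via email to a videoconference" concerns the screening call. Participants are then sent a study laptop, which is recalled on withdrawal.

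**Conclusion.** The concern holds and should be fixed before analysis. This is a stated rule that restricts the primary comparison by attendance after randomisation, with nothing elsewhere that clearly reverses it. It is more than missing detail.

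The rule is certain, but the size and sign of its effect are not. Bias is zero if exclusion is balanced in share and prognosis. Under the assumptions above, bias from uneven exclusion is about 3% to 11% of the 12-point design difference at 15% versus 5% (0.4/12 to 1.33/12). It reaches 21% (2.52/12) only when 25% versus 5% exclusion, a correlation of 0.5 with outcome and no relation to baseline all coincide. Counting over 15 visits instead of per block raises the excluded share by about 1.3 to 2.8 times, depending on how strongly misses cluster within persons. A reader might infer that the trial's result will be biased. The documents show only that it is exposed to bias they give no means of bounding.

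**What to change.** - Delete the clause that withdraws these participants from the analysis. State that the primary Aim 2 analysis includes every randomised participant in the assigned arm, regardless of missed visits.
- Seek the already planned remote 6- and 12-month evaluations from people who stop study sessions.
- Name one method for absent 12-month scores, for example the planned analysis of covariance with multiple imputation, and add a sensitivity analysis for its missing-data assumption.
- Keep the attendance-based exclusion as a labelled sensitivity analysis.
- Have the sponsor reconcile the triggers in Scheduling Compliance and Withdrawal of Participants, the counting basis (per block or over 15 visits) and the data-use sentences. This review takes no position on which trigger is right.

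The cost is revised protocol and analysis wording, and probably revised consent wording, since withdrawal reasons are stated in the consent form. There would be a few extra remote evaluations of up to 4 hours each, and later laptop retrieval for those people. The estimate would also be somewhat diluted by non-adherers.

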PROTOCOL TITLE: Communication Bridge: A person-centered Internet-based intervention for individuals with primary progressive aphasia

NCT NUMBER: NCT03371706

VERSION NUMBER: 12.0

VERSION DATE: July 3, 2023

PROTOCOL TITLE: Communication Bridge: A person-centered Internet-based intervention for individuals with primary progressive aphasia

PRINCIPAL INVESTIGATOR: [name] [name] [contact]

NCT NUMBER: NCT03371706

VERSION NUMBER: 12.0

VERSION DATE: March 27, 2020

OBJECTIVES:

The proposed study will use a randomized controlled trial (RCT) design to evaluate whether a person-centered treatment (experimental) for adults with mild PPA maximizes functional communication participation as compared to an impairment-only treatment (control). All treatment will be provided remotely by speech language pathologists using a HIPAA compliant video-conferencing program.

Aim 1: Determine the within-group response of the Experimental and Control treatments for individuals with PPA.

- Aim 1a: To provide descriptive and quantitative characterizations of within-group responses to treatment. This data will serve to inform future clinical study design.
 - Hypothesis 1: The experimental group will show significant within-subject gains on communication participation and language performance measures, while control group gains will be restricted to language performance measures.
- Aim 1b: Determine if the magnitude of treatment response is mediated in part by participant home exercise compliance, PPA subtype, level of depression, and/or communication partner support.
 - Hypothesis 2: We hypothesize the number of times participants complete their home exercises (i.e., compliance) will be a significant mediating factor in treatment response, especially for the language performance measures.

Aim 2: Determine if a person-centered dynamic treatment approach (experimental) for adults with PPA will show more favorable communication participation outcomes as compared to a dose-matched impairment-only treatment approach (control) over a 12-month course of disease.

• Hypothesis 3: Participants in the experimental group will show more favorable communication participation outcomes relative to the control group.

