Aim 1: Determine the within-group response of the Experimental and Control treatments for adults with PPA. Aim 1a will provide a descriptive and quantitative characterization of the response to treatment including within- group effect sizes.

Statistical analysis Aim 1a: The primary analysis goals for Aim 1a will be (i) the estimation of the within-person change and the variability in this change along with the statistical significance of the change within each treatment group and (ii) the estimation of the within-group effect size for each treatment group. These analyses will be done for all outcomes.

Power calculation for Aim 1: In preliminary data, the Pearson correlation between the initial and 6 month CCRSA was 0.70. Assuming a standard deviation of σ for an outcome at one time, and assuming a correlation of 0.50 between the initial and 12 month measure (since follow-up is longer), then the standard deviation of the change is also σ . Similar assumptions will be made for all outcomes. The Experimental group with a sample size of 51 would have 80% power to detect a mean change that is 0.4 σ while the Control group with a sample size of 34 would have 80% power to detect a mean change of 0.5 σ . For testing correlations between the change in an outcome and a continuous measure, the Experimental group (n=51) would have 80% power to detect a correlation of 0.38 while the Control group (n=34) would have 80% power to detect a correlation of 0.46. Two-tailed tests and a Type I error rate of 5% are assumed for all calculations for Aim 1.

Aim 2: Determine if a person-centered dynamic treatment approach (Experimental) for adults with PPA will show more favorable communication participation outcomes as compared to an impairment-only treatment approach (Control) over a 12-month course of disease.

Specific Aim 2 Analysis: The group statistical analysis will focus on two participation measures (CCRSA, Goal Attainment Scaling [GAS]) and two language performance measures (% target word accuracy and % script accuracy). All outcomes are continuous measures except for GAS which is ordinal. The primary analyses will focus on the initial and 12-month time points. Secondary analyses will be done using all time points, specifying certain post-hoc comparisons of interest (e.g. comparing the effect of the preand post-evaluations for the 6-month Treatment Sessions between groups).

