Power Calculation for Aim 2: Power will be based on a sample size of 51 in the Experimental arm and 34 in the Control arm. For all language and participation outcomes, preliminary data were used to estimate unadjusted standard deviations (SDs). It is expected that analysis of covariance would reduce the unadjusted SDs but since longitudinal data were not available on all measures, the conservative approach will be to use the unadjusted SDs in the power calculation. The Table below gives the between-group effect size (in units of the scale) detectable with 80% power for each outcome measure using a two-tailed test and a Type I error rate of 0.017. For example, for the CCRSA scale, there is 80% power to detect an Experimental minus Control difference of 12% in the 12-month mean adjusted by analysis of covariance for the initial evaluation CCRSA level.

Measure	Туре	SD	Between-group effect size with n=51 and 34 per arm ^A
Lexical Retrieval	Language	19 16	13
Script Performance	Language	14 25	10
Confidence Rating Scale for Aphasia (CCRSA)	Participation	16 16	12
Goal Attainment Scaling (T-Score)	Participation	10 26	7
^A 80% power, 2-tailed p<0.025 for language measures and $p<0.017$ for participation measures			

Table 1. Power Calculations

All members of the study team will be trained on the procedures of how data are stored and managed. Members of the study team that are approved by the Northwestern IRB will have access to the REDcap database and to the web-application database. All access to these applications will be provided over encrypted-TLS communication and all servers are locked and managed in a physically secure facility with Marlok identity management. All data will be de-identified and stored as much.

All data will be checked by a research assistant who is different from the individual who administered the tests. This checking will take place on hard copies of outcome measures and data stored in REDcap. Discrepancies between raters will be recorded by a crossing out of original score and initialing the new score with the checkers initials. REDcap includes a feature where data can be marked as "unchecked" or "checked". Once data are checked by a second scorer, they will be marked as "checked" in REDcap.

Participants will be asked if they are willing to share data from the study with other researchers within the CNADC. If so, researchers will not receive any identifiable information.

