By participating in this study, participants will learn new strategies for coping with their communication difficulties caused by the disease. These new strategies may allow the individuals to engage more actively in their lives by facilitating communication. In our pilot study, we saw increased communication confidence when comparing post-treatment measures of the CCRSA to pre-treatment measures. We also found that this increase in performance was maintained 6-months post-treatment. However, due to the progressive nature of the disease, individual's communication will get worse over time. This current study is important in determining the duration of potential benefits beyond this point.

VULNERABLE POPULATIONS:

Individuals with Primary Progressive Aphasia are cognitively impaired. However, individuals in the mild stages of Primary Progressive Aphasia have deficits primarily in the use of language. Memory, attention, and other cognitive abilities are preserved. Individuals enrolled in this study will be verified as being in the mild stages of the disease through medical records and a brief evaluation by our team. Additionally, participants with PPA will be consented with their communication partner. Their communication partner will also be consented into the study. This

study provides an intervention for a population that has no pharmacological treatment for their disease, and thus a benefit for them to more effectively cope with their symptoms.

Individuals will be provided with the opportunity to speak with members of the study team, including speech-language pathologists, prior to consent and enrollment to ask any questions they have. The study team members, including SLPs, are trained in communicating with individuals of this population. We believe that these steps will ensure that the participants (patient and communication partner) have sufficient information to participant in the study.

COMMUNITY-BASED PARTICIPATORY RESEARCH:

n/a

SHARING OF RESULTS WITH PARTICIPANTS:

Results will not be shared with the participants.

SETTING:

The research team will be located at the Mesulam Center for Cognitive Neurology and Alzheimer's Disease. This is where all consent forms and data from the study will be stored. Speech language pathologists that provide treatment for the study will come from Northwestern University and Oregon Health and Science University.

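### The primary Aim 2 comparison uses only the initial and 12-month visits and has no missing-data method, so participants without a 12-month score do not enter it even when intermediate scores exist

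*Combined protocol and SAP*

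**What the plan says.** Aim 2 (OBJECTIVES) compares the person-centred arm "as compared to a dose-matched impairment-only treatment approach (control) over a 12-month course of disease". Under PROCEDURES INVOLVED, each participant has an initial evaluation and four later ones: Post-Intervention 1, 6 months, Post-Intervention 2 and 12 months.

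Under DATA AND SPECIMEN MANAGEMENT, Specific Aim 2 Analysis, the plan says "The primary analyses will focus on the initial and 12-month time points", and directly afterwards "Secondary analyses will be done using all time points, specifying certain post-hoc comparisons of interest". The same section calls three of the four outcomes continuous and Goal Attainment Scaling (GAS) ordinal.

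The primary model is named only in Power Calculation for Aim 2: "there is 80% power to detect an Experimental minus Control difference of 12% in the 12-month mean adjusted by analysis of covariance", with the initial CCRSA level as covariate.

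Under WITHDRAWAL OF PARTICIPANTS, "Participants can be withdrawn from the study for the following reasons: 1) Lost contact"; missed visits or scheduling breaches and outside speech-language therapy follow. That section ends: "Data collected up until the point of lost contact with the participant will be used in analyses for the study". It does not say which analyses are meant.

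Neither the analysis text nor any other section gives a missing-data method, a primary analysis population, an expected dropout rate or a sensitivity analysis.

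**The concern.** An analysis of covariance of the 12-month score on the initial score needs both scores. Without a stated way to handle a missing 12-month score, a participant lost after Block 1, after month 6 or after Block 2 falls out of the primary comparison, and what was learned about that person's course is set aside.

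This matters more than usual here. The protocol itself says that, "due to the progressive nature of the disease, individual's communication will get worse over time". If those whose scores are already falling are more likely to be lost, the people seen at month 12 are a better-off subset. The treatment comparison is distorted when this selection differs by arm. That happens if loss is tied to decline more strongly in one arm. It also happens if the mechanism is the same in both arms but one arm declines more and so loses more of its worst cases. The arms also place different demands on families: communication partners attend every session in the experimental arm, but only the first session and part of later ones in the control arm (PROCEDURES INVOLVED, Study Design). Loss that differs by arm is therefore a realistic possibility.

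**Working it through.** **1. Who enters the primary comparison.** The outcome is the 12-month score and the covariate is the initial score. With the 12-month score missing and no imputation or likelihood method stated, the record cannot be used. The three intermediate post-baseline scores do not appear in the model.

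**2. The plan's own figure.** Inputs from Power Calculation for Aim 2 and Table 1: n = 51 and 34, CCRSA SD 16 (unadjusted), two-sided alpha 0.017, power 80%.

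- SE = 16 × √(1/51 + 1/34) = 3.54
- Detectable difference = 3.54 × (2.387 + 0.842) = 11.44 by the normal approximation, and 11.64 by the noncentral t

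Table 1 prints 12. The noncentral-t values for the other outcomes also round to the printed figures: GAS 7.27 (7), lexical retrieval 13.17 (13), script 9.70 (10). The table's arithmetic is sound.

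**3. Does loss threaten power?** The basis of 51 + 34 = 85 is not explained. If it means 12-month completers (an assumption), it equals 90 less 5.6% (5/90) or 100 less 15% (15/100). Power for a CCRSA difference of 12, counting completers only and split 60:40:

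| Lost by month 12 | From 90 | From 100 |
|---|---|---|
| 15% | 0.796 | 0.842 |
| 20% | 0.768 | 0.816 |
| 30% | 0.702 | 0.754 |

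Using the 0.50 correlation that the plan assumes between initial and 12-month scores (Power calculation for Aim 1), the adjusted SD is 16 × √(1 − 0.50²) = 13.86. Power at 30% loss is then 0.837 from 90 and 0.878 from 100. Power is not the main issue.

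**4. Can loss bias the estimate?** The documents give no dropout rate or mechanism, so every input below except SD and correlation is assumed.

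*Same mechanism in both arms.* n = 51 and 34; SD 16; correlation with the initial score decaying exponentially to 0.50 at month 12; visits at 0, 3, 6, 8 and 12 months. Experimental means are 68, 73, 71, 70, 68 and control means 68, 68, 64, 61, 56, a true 12-month difference of 12. Before each visit from month 6 on, the log-odds of loss are b0 + b1 × (last observed decline ÷ 16). There were 3,000 replicates.

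| b0, b1 | Lost, exp / control | Completer ANCOVA | All-visit likelihood |
|---|---|---|---|
| −4, 0 | 5% / 5% | 11.97 | 11.95 |
| −4, 1 | 6% / 9% | 11.87 | 12.02 |
| −3, 1 | 14% / 20% | 11.59 | 11.98 |
| −2.5, 1 | 21% / 29% | 11.44 | 11.98 |
| −3, 2 | 18% / 32% | 10.60 | 11.98 |

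Where loss depends on decline, the completer estimate is short by 12 − 11.87 = 0.13 up to 12 − 10.60 = 1.40 points. When both arms were given the control means (true difference 0; 1,500 replicates), both methods stayed within about 0.13 of zero.

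*Mechanism differing by arm.* n = 54 and 36, SD 16, correlation 0.50, true difference 0, loss after month 6 tied to observed decline in the control arm only; 3,000 replicates. With retention 86%/80% the completer bias was −1.8 points. With a stronger link and retention 85%/66% it was −3.5 points, about one standard error. The all-visit likelihood estimate showed a bias of 0.0 in both. If decline drives loss in the experimental arm instead, the sign reverses and the bias favours that arm.

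**The case against.** Three stronger readings are tempting, and the documents support none of them.

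- **That the plan contradicts itself on using data from people lost to contact.** The withdrawal section promises use in the study's analyses without saying the primary one. The planned all-time-point secondary analyses can honour that promise. The sentence needs clarifying; it is not broken.
- **That those who decline are the ones who will be lost.** Decline is not among the listed withdrawal reasons. The protocol's own evidence is fairly reassuring: enrolment is limited to mild disease, pilot CCRSA showed no significant decline at 6 months, 13% fell one level on the ASHA-FCM at 6 months, and retention in the centre's PPA research programme is described as excellent. Decline-related loss is plausible, not documented.
- **That the plan chose a completers-only analysis.** It never says so. The wording on the two time points is not exclusive, and analysis of covariance is named only in the power text. Exclusion follows from the model described combined with silence on missing data. That stands as a gap, because nothing in the plan offers incomplete cases another route into the primary comparison.

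The bias is also small when loss is modest: about 0.1 point at 6–9% loss. Finally, the simulated loss depends only on observed scores, so the likelihood method is bound to do well. Its near-zero bias shows what it achieves if that assumption holds, not that the assumption holds in this trial. This point stands in full and is why a further sensitivity analysis is needed.

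**Conclusion.** The concern holds in a limited form. The primary Aim 2 comparison, as described, leaves out anyone without a 12-month score and ignores intermediate scores that the trial collects anyway. No method for missing data is stated. Across the assumed scenarios with decline-related loss, the resulting bias runs from about 0.1 to 3.5 CCRSA points. That is 1% (0.1/12) to 29% (3.5/12) of the planned difference of 12, and up to about one standard error. The upper end requires about a third of the control arm to be lost, with loss tied to decline in that arm alone. The direction is not fixed: it depends on which arm's loss is tied to decline. There is no material bias if mechanism and outcomes are the same in both arms.

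These sizes rest on assumed means, dropout rates and mechanisms that the documents do not supply. Table 1 is not at fault. The change is worth making because it is cheap and protects the primary estimate, not because bias has been shown to exist.

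**What to change.** Keep the 12-month treatment difference as the primary estimate and change how it is obtained.

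- **Continuous outcomes (CCRSA, target-word accuracy, script accuracy):** a likelihood-based repeated-measures model on all four post-baseline evaluations, with initial value, visit, arm and arm-by-visit, and unstructured covariance. Include every randomised participant with at least one post-baseline value, and read the primary result from the 12-month contrast.
- **GAS:** an ordinal repeated-measures counterpart, or the same model on the T-score with that choice justified, since the analysis text calls GAS ordinal.
- **Sensitivity analyses:** the two-visit analysis of covariance, and one that allows loss to depend on decline that was not observed.
- **Text:** state the primary analysis population and which analyses the data-use sentence under WITHDRAWAL OF PARTICIPANTS covers. In doing so, reconcile it with Scheduling Compliance, where after more than two missed visits "the participant will be withdrawn from the study analysis".

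The cost is plan wording and slightly more analysis work. No new data are needed, and all-time-point analyses are already intended. The model relies on loss being explained by observed scores, and it still leaves out anyone lost before Post-Intervention 1; the plan should say both.
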